4.2. Prohibited Medications and Procedures

No concomitant prescription medications, over-the-counter medications, medical foods, and nutritional supplements are to be started, or doses changed during the study unless they are prescribed by the subject's primary care giver for treatment of a specific clinical event.

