4.3. Rescue Medications

Acetaminophen, may however, be used for mild headache or myalgia at a dose of 650 mg three times daily as needed.

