7.1. Definition of an adverse event (AE)

An AE is any unanticipated or unintended medical occurrence or worsening of a sign or symptom (including an abnormal laboratory finding) or disease in a study subject, including those events which do not necessarily have a causal relationship with the study condition, procedures or Study Product(s), that occurs after the informed consent is obtained.

Pre-existing conditions or illnesses which are expected to exacerbate or worsen are not considered adverse events and will be accounted for in the subject's medical history.

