7.4.3. Modification of Study Product(s)/Intervention(s) for a Subject

No food substitutes are permitted. A reduction of food products, a hold of food or discontinuation of food product is allowed at the discretion of the study clinician.

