7.4.5. Stopping Rules for an Individual Subject

A study subject will be discontinued from further Study Product(s) administration for:

a significant reduction of BMI greater than 15% from baseline measurement and in any case of a BMI measurement lower than 22 Kg/m² for women and 23 Kg/m² for men during the follow-up visits; any clinical adverse event, laboratory abnormality, concurrent illness, other medical condition.

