7.7. Study Discontinuation

The study will be discontinued for the following reasons:

- any clinical adverse event or serious adverse event, laboratory abnormality or inter-current illness which, in the opinion of the PI, indicates the continued treatment with study therapy is not in the best interest of the subjects.
- Termination of the study by the Sponsor.

8. Statistical Analysis plan

8.1.

All participants meeting the inclusion criteria will be considered. Based on the current drop-out rate of 21% and 18%, for FMD or FMD+LD, respectively, observed during the completed study “**Studio degli effetti della dieta mima-digiuno e della dieta longevità sulla composizione corporea, fattori di rischio per malattie età-correlate e marcatori dell'invecchiamento in uno studio randomizzato**” and assuming a similar drop out in the study: **Studio degli effetti della dieta mima-digiuno e della dieta longevità sulla composizione corporea, fattori di rischio per malattie età-correlate e marcatori dell'invecchiamento in uno studio randomizzato-2**” not yet completed, we can hypothetical foresee a maximum number of subjects of 267.

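### The individual stopping rule in 7.4.5 has no qualifier for severity, relatedness or judgement, and so contradicts the clinician's discretion in 7.4.3

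*Protocol*

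**What the plan says.** Protocol 7.4.5 opens with mandatory wording: "A study subject will be discontinued from further Study Product(s) administration for". After a criterion on BMI, which is not at issue here, it lists "any clinical adverse event, laboratory abnormality, concurrent illness, other medical condition". Nothing limits that list by grade, by relation to product or by anyone's judgement.

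Other sections deal with the same situation differently:

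- **7.4.3** states: "A reduction of food products, a hold of food or discontinuation of food product is allowed at the discretion of the study clinician".
- **7.3.3**, in its highest causality category, provides for re-challenge where necessary.
- **4.3** says of one medicine that it may "be used for mild headache or myalgia".
- **4.2** bars new or changed medication "unless they are prescribed by the subject's primary care giver for treatment of a specific clinical event".
- **7.7**, on stopping the whole study, gives a similar list but limits it to events "which, in the opinion of the PI, indicates the continued treatment with study therapy is not in the best interest of the subjects".

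Two definitions set the reach of 7.4.5. Section 7.1 counts as an adverse event any occurrence that is unanticipated or unintended, including abnormal laboratory findings and events with no causal link to product. It leaves out the expected worsening of pre-existing conditions. Section 7.3.2 counts as mild an event that needs little or no treatment and does not disturb daily life.

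**The concern.** Read as written, a mild and unrelated event that needs no treatment obliges the site to end the intervention for that participant. Section 7.4.3 tells the same site that it may reduce or hold product instead. Staff cannot obey both, and the protocol does not say which prevails.

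This affects the result as well as site conduct. The primary endpoint (2.2.1) is retention of at least half of the fat mass lost in the parent trial, measured after a year of quarterly cycles. If the rule is applied literally, some participants will not receive that year of cycles, for reasons that may be trivial. If it is applied loosely, each clinician decides by a private standard, and the group remaining on product is shaped by tolerance in a way that nobody has specified. No concurrent control arm would reveal such selection: 8.6 compares with the control arm of the previous study. Section 7.4.7 also allows subjects who discontinue treatment to be replaced at the PI's discretion.

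**Working it through.** **Step 1: the passages side by side**

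| Section | What follows after a mild adverse event | Fit with 7.4.5 |
|---|---|---|
| 7.4.5 | Product must be stopped | – |
| 7.4.3 | Clinician may reduce, hold or discontinue | Direct conflict: two of the three options are closed |
| 7.3.3 | Re-challenge may be used to grade causality | Poor fit: re-challenge means giving product again |
| 4.3, 4.2 | Symptom or event may be treated on study | Conflict by implication only: neither says the subject stays on product |
| 7.7 | Study stops only if the PI judges that continuing is not in subjects' interest | Poor fit: the rule for one subject is stricter than the rule for the whole study |

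**Step 2: how often the trigger is tested.** Under 3.3, participants are telephoned on day 6 of each cycle and asked about adverse events, so the clinical trigger is checked after every cycle. The laboratory trigger is not. Table 1 schedules haematological analyses at baseline and T2 only, and T2 comes after the fifth cycle, so scheduled laboratory results add little before then.

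**Step 3: the plan's own number.** Section 8.1 gives a maximum of 267 subjects. With 167 per intervention arm (1.2) and parent-trial drop-out of 21% and 18% (8.1):

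- 167 × (1 − 0.21) = 131.93, rounded down to 131
- 167 × (1 − 0.18) = 136.94, rounded down to 136
- 131 + 136 = 267, which reproduces the stated figure.

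The drop-out rates therefore describe who is left from the parent studies. They are not an attrition allowance for this study.

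**Step 4: share stopped under the literal rule.** The follow-up visits come after three and five cycles, so there are five cycles. An event reported after the fifth leaves no product to stop, so four cycles count. Let p be the probability of at least one adverse event per cycle. The protocol gives no value, so p is assumed, and cycles are taken as independent:

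share stopped before cycle 5 = 1 − (1 − p)⁴

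| Assumed p | Calculation | Share stopped | Of 267 |
|---|---|---|---|
| 1% | 1 − 0.99⁴ | 3.9% | about 11 |
| 5% | 1 − 0.95⁴ | 18.5% | about 50 |
| 10% | 1 − 0.90⁴ | 34.4% | about 92 |
| 20% | 1 − 0.80⁴ | 59.0% | about 158 |

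Solving for p, a quarter would be stopped at p = 1 − 0.75^(1/4) ≈ 6.9%, and half at p = 1 − 0.5^(1/4) ≈ 15.9%.

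If events cluster in the same people, the share for a given average p is lower than shown. Concurrent illness between cycles, a separate trigger in 7.4.5, would raise it.

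**The case against.** The strongest reply is that this is a drafting slip with little practical effect. The similar list in 7.7 carries a judgement clause, which suggests that one was meant in 7.4.5. Participants have completed a parent trial that included FMD, so their event rates may be low. That is plausible, but a dropped clause is an inference and the text as it stands is mandatory. Low rates reduce the number affected without resolving the conflict with 7.4.3.

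Four stronger readings are tempting, and the objection is right to resist them:

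- A reader might infer that the rule would stop a large share of participants. The protocol gives no adverse-event rate, and the result runs from about 4% to 59% over the rates assumed above.
- A reader might set these shares against the 18% to 21% drop-out in 8.1. Those rates are parent-trial attrition used to reach 267, and stopping product is not the same as dropping out.
- A reader might say that 4.3 flatly contradicts 7.4.5. Symptoms can be treated whether or not later cycles go ahead, so the conflict is only implied.
- A reader might infer that a participant who stops product also leaves follow-up. Section 7.4.5 ends product only, and Table 1 makes no exception for such participants. How they enter the primary analysis may be left to the SAP, which is not at hand.

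**Conclusion.** The contradiction between 7.4.5 and 7.4.3 is in the text and rests on no assumption. The mismatch with 7.3.3, 4.2, 4.3 and 7.7 is real but weaker. What the protocol fixes badly is the rule itself: it is mandatory, unqualified and tied to a broad definition of adverse event, so a mild or unrelated event meets it.

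The size is conditional. For assumed per-cycle probabilities of 1%, 5%, 10% and 20%, independent across cycles, about 4%, 19%, 34% and 59% would be stopped before the fifth cycle under the literal rule. The documents support no single figure in that range. Under a loose reading the number cannot be calculated, because the criterion is then whatever each clinician applies. The point should be corrected, but it does not by itself invalidate the design.

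**What to change.** Amend the protocol so that 7.4.5, 7.4.3, 7.3.3, 4.2, 4.3 and 7.7 express one rule for when an individual stops product and who decides. Which rule that should be is a clinical matter for the sponsor.

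In the same amendment, state that stopping product does not end the assessments already in Table 1: BIA at T1 and T2, and bloods at T2. No blood is scheduled at T1, and none need be added for this purpose.

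The cost is a wording change, submitted for ethics approval as 9.2 requires for amendments. It adds no visits or procedures to the schedule.

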7.4.6. Premature Withdrawal of a Subject

A subject may decide to withdraw informed consent for any reason. Premature discontinuation by a subject will be evaluated to assess the status of the subject at termination, and will be recorded in the subject's medical record and in the CRF.

7.4.7. Replacement of a Subject Who Discontinues Study Treatment

Subjects may be replaced at the PI's discretion.

7.5. Research Use of Stored Human Samples, Specimens or Data

7.5.1. Use of Stored Data

Any other research or experimental treatments will be done under additional protocols for which separate signed informed consent documents will be obtained.

7.5.2. Disposition of Stored Samples and Data

Data will be stored using codes assigned by the investigators. Data will be kept in password-protected computers. Only authorized members of the study team will have access to the samples and data.

7.5.3. Assent or Informed Consent Process in Case of a Minor

Minors are excluded from this study.

7.6. Subject Confidentiality

The investigator will ensure that the subject's anonymity is maintained. Subjects will not be identified in any publicly released reports of this study. All records will be kept confidential to the extent provided by federal, state and local law. The study monitors and other authorized representatives of the Sponsor may inspect all documents and records required to be maintained by the Investigator, including but not limited to, medical records.

The investigator will inform the subjects that the above-named representatives will review their study-related records without violating the confidentiality of the subjects. All laboratory specimens, evaluation forms, reports, and other records that leave the site will be identified only by a coded number in order to maintain subject confidentiality. All records will be kept locked and all computer entry and networking programs will be done with coded numbers only. Clinical information will not be released without written permission of the subject, except as necessary for monitoring by the FDA, the Sponsor, or the sponsor's designee.

7.7. Study Discontinuation

The study will be discontinued for the following reasons:

- any clinical adverse event or serious adverse event, laboratory abnormality or inter-current illness which, in the opinion of the PI, indicates the continued treatment with study therapy is not in the best interest of the subjects.
- Termination of the study by the Sponsor.

8. Statistical Analysis plan

8.1.

All participants meeting the inclusion criteria will be considered. Based on the current drop-out rate of 21% and 18%, for FMD or FMD+LD, respectively, observed during the completed study “**Studio degli effetti della dieta mima-digiuno e della dieta longevità sulla composizione corporea, fattori di rischio per malattie età-correlate e marcatori dell'invecchiamento in uno studio randomizzato**” and assuming a similar drop out in the study: **Studio degli effetti della dieta mima-digiuno e della dieta longevità sulla composizione corporea, fattori di rischio per malattie età-correlate e marcatori dell'invecchiamento in uno studio randomizzato-2**” not yet completed, we can hypothetical foresee a maximum number of subjects of 267.

8.2. Study Records Retention

The PI will retain investigational product disposition records, electronic database files, and source documents for the maximum period required by applicable regulations and guidelines, or as specified by the Sponsor, whichever is longer. Records with individual patient identifiers will be maintained for 10 years only. After this date, all records will be identified by subject number only with no connection to individual patients. The Sponsor will inform the PI when records are no longer needed.

8.3. Clinical Monitoring Plan

Representatives of Sponsor will be allowed to visit the study site periodically to assess the data, quality and study integrity. This will include reviewing study records, compare records with source documents, discussing conduct of study with the PI and verifying the conditions of the facility. In addition, the study may be evaluated by Sponsor's auditors and government inspectors. They will be allowed access to source documents, electronic database, and other study files.

8.5. Safety Review

A review of the collected safety data will be ongoing by the study coordinator. These reports will be reviewed by the PI.

8.6. Study conclusions

Collected data from subjects will be reviewed to demonstrate that favourable changes are noted in biomarkers of body composition and age-related biomarkers with administration of the proprietary food products. Data will be evaluated for change from baseline over time within arms and for differences between the intervention arm and the control arm of previous study.

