1.2. Fasting Mimicking Diet

The fasting-mimicking diet (FMD) is a 5-day meal program to be consumed every 1 to 6 months based on an authorized healthcare professional's recommendation. It is designed to promote the body's natural ability to protect, regenerate and rejuvenate itself. In clinical studies, FMD has been shown to reduce abdominal fat and maintain healthy levels of blood glucose, C-reactive protein (CRP), and insulin-like growth factor 1 (IGF-1) (Wei et al., 2017). Well-designed clinical trials, such as the study conducted by Houston et al. utilizing an independent review board (IRB) approved protocol, have demonstrated the safety and short-term benefits of plant-based nutraceuticals and food restriction in individuals with chronic hypertension (Houston et al., 2014).

A large ongoing randomized, open-label trial aimed at evaluating the effects of two different dietary interventions, FMD and LD, on body composition and cardiovascular (CV) biomarkers in a real word population (NCT05698654) is actually ongoing. This trial started in January 2024 will enrol 501 adult subjects between the ages of 30 and 65: 167 subjects randomized to the FMD arm with a 5-day meal program once every three months for a 6-month period (arm 1); 167 subjects randomized to follow the FMD plus a Longevity Diet program (FMD+LD) for a 6-month period (arm 2); 167 randomized to the control group (arm 3) that will continue their usual diet. On 2024,410, participants were enrolled and randomly assigned to FMD, FMD + LD, or control arm. Although preliminary data demonstrated the beneficial effects of such nutritional plans on body weight, BMI, body composition, and cardiovascular (CV) biomarkers, limited data is available on the long-term effects of these powerful nutritional interventions.

2. Study Objectives/Endpoints

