2.2. Endpoints

- 2.2.1. *Primary endpoint*: maintenance of at least 50% of the fat mass lost during the previous trial and measured after one follow up year on FMD every 3 months
- 2.2.2. *Secondary endpoints*: maintenance of at least 50% of one or more risk factors improvements achieved during the previous clinical trial and measured after one year of follow up FMD cycles every 3 months including improvements in: body mass, body mass index, blood pressure, IGF-1, haemoglobin A1c, fasting glucose, LDL, total cholesterol, and C-Reactive Protein. Determine long-term trends in the reduction/stabilization in the use of antihypertensive and glucose-lowering drugs or other commonly used medications.

3. Study Design

Follow up clinical trial including participants of the approved studies “*Studio degli effetti della dieta mima-digiuno e della dieta della longevità sulla composizione corporea, fattori di rischio per malattie età-correlate e marcatori dell'invecchiamento in uno studio randomizzato*” and “*Studio degli effetti della dieta mima-digiuno e della dieta della longevità sulla composizione corporea, fattori di rischio per malattie età-correlate e marcatori dell'invecchiamento in uno studio randomizzato-2*” that will follow 5-day of the FMD meal program every three months, for one year.

Selection and withdrawal of subjects of the previous clinical study

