3.1.1. Inclusion Criteria

Individuals already included in the aforementioned previous studies *who were assigned to one of the 2 intervention arms: Fasting mimicking diet or fasting mimicking diet plus Longevity diet* and who completed the study less than 6 months prior to starting the new study. Blood tests and a nutritional assessment will be conducted, serving as the baseline for the new study.

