- Any sound medical, psychiatric and/or social reason which, in the opinion of the PI, would preclude safe participation in this study or interfere with compliance.
- Abnormal laboratory findings including: abnormal blood counts (haematocrit < 33% or > 47%; WBC < 3.0 or > 12.0 $\times 10^3/\text{mm}^3$; platelets < 140 or > 500 $\times 10^9/\text{L}$); abnormal kidney function test (creatinine > 2.5 mg/dL) or liver function test(s) (AST, ALT, alkaline phosphatase) > 1.5X the upper limit of normal; serum calcium > 11 mg/dL; serum K < 3.5 mEq/L; Na < 134 or > 148 mmolL⁻¹

3.1.8. *Women of Childbearing Potential*

Contraception: the effects of the study products on the developing human fetus have not been studied extensively. For this reason, women of childbearing potential must agree to use adequate contraception (hormonal or barrier method of birth control; abstinence) prior to study entry and for the duration of study participation. Females of childbearing potential will have a pregnancy test prior to receiving study products. Should a woman become pregnant or suspect she is pregnant while participating in this study, she should inform study staff and her primary care physician immediately.

Pregnancy: because there is an unknown but potential risk for adverse events in pregnant women during treatment with the study products, pregnant women are not eligible for study participation.

Breast-feeding: Because there is an unknown but potential risk for adverse events in nursing infants secondary to treatment of the mother with the study products, breastfeeding mothers are not eligible for study participation.

3.2. *Recruitment*

The participants will be identified within the intervention groups of the previous clinical studies (*Studio degli effetti della dieta mima-digiuno e della dieta della longevità sulla composizione corporea, fattori di rischio per malattie età-correlate e marcatori dell'invecchiamento in uno studio randomizzato 1 and 2*) who are willing to start a new study for other 12 months, and who completed the study less than 6 months prior to starting the new study and achieved the study's objectives. Blood tests and a nutritional assessment will be conducted, serving as the baseline for the new study. The recruitment period will last up to 3 years

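### Section 8.6 plans a comparison with the previous trial's control arm, but the protocol describes no control data for this study's 12-month period

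*Protocol*

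**What the plan says.** Protocol section 8.6, Study conclusions, plans two kinds of evaluation: change from baseline within arms, and "differences between the intervention arm and the control arm of previous study".

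The parent trial is described in section 1.2. The first intervention arm is "167 subjects randomized to the FMD arm with a 5-day meal program once every three months for a 6-month period (arm 1"). The second adds the Longevity Diet, also for 6 months. The third is "167 randomized to the control group (arm 3) that will continue their usual diet"; no follow-up length is given for it. Section 3 names two parent studies, and no separate duration or control follow-up is stated for the second.

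The present study takes people "who were assigned to one of the 2 intervention arms" and "who completed the study less than 6 months prior to starting the new study" (section 3.1.1). Section 3.2 adds that they must be willing to take part for a further 12 months, and places the completion window "prior to starting the new study and achieved the study's objectives". The design in section 3 is one of participants "that will follow 5-day of the FMD meal program every three months, for one year". The primary endpoint in 2.2.1 is "measured after one follow up year on FMD every 3 months". Section 3.3 gives eligible participants visits at baseline, 6 and 12 months, and the baseline is newly measured at entry.

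**The concern.** A comparison between arms needs control values for the period over which the intervention is judged. Here that period is the 12 months after a new baseline, and nobody outside the former FMD and FMD+LD arms enters or is visited during it. The only control values that could be used come from the parent study and belong to an earlier period with a different baseline.

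The sentence stands under the heading of study conclusions, next to the aim of demonstrating favourable changes with the food products. A difference from the old controls could therefore be reported as a long-term effect of FMD. Because the control group was once randomised, a reader could also credit the comparison with a protection that it no longer has.

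**Working it through.** **Step 1. Who can be in the data.** Section 3.1.1, section 3.2 and the Screening and Baseline visit text all restrict entry to the two former intervention arms. Section 3.3 schedules visits for eligible participants only. Former controls eligible: 0. Control measurements planned at T0, 6 or 12 months: 0.

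**Step 2. The plan's own number.** Section 8.1 gives a maximum of 267, using drop-out of 21% (FMD) and 18% (FMD+LD). With 167 per arm from section 1.2:

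- FMD: 167 × (1 − 0.21) = 131.93
- FMD+LD: 167 × (1 − 0.18) = 136.94
- Sum: 268.87; rounding each arm down, 131 + 136 = 267

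The stated maximum is thus reproduced from the two FMD arms with no contribution from controls. This only corroborates step 1, since the eligibility text already settles the matter.

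**Step 3. Timing.** Let *g* be the gap in months between parent completion and the new baseline. From 3.1.1 and 3.2, 0 ≤ *g* < 6. Section 1.2 gives 6 months for the parent intervention, and the final visit is at 12 months.

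- Final visit, counted from the parent baseline: 6 + *g* + 12 = 18 to under 24 months.
- Assumption: controls were followed for 6 months, like the intervention arms. Their last value would then precede the participant's final value by *g* + 12 = 12 to under 18 months.

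The assumption is needed because section 1.2 gives no length for the control arm. The figures also apply to the second parent study only if it ran to the same length.

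**Step 4. Which filters each group passed.**

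| Filter | Entrants | Parent controls |
|---|---|---|
| Completed the parent study | Required (3.1.1, 3.2) | Would hold for controls with end-of-study data |
| Willing to continue for 12 months | Required (3.2) | Not applied |
| Met the parent study's objectives | Stated in 3.2; absent from 3.1.1 and from the screening text | Not applied |

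The parent randomisation balanced everyone assigned. It does not balance a subset selected on one side by willingness, and possibly by outcome, against a group that was not selected in the same way. If the outcome filter in 3.2 is used, entrants are chosen partly because they did well from the parent baseline. A comparison measured from that baseline would then tend to favour FMD. The documents give no basis for a size.

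**Step 5. Where the old control arm is used.** The objectives (2.1) and endpoints (2.2) concern maintenance within participants. The model in 8.6.1 has a term for change from baseline to the 12-month visit and a random term for repeated measurements on a participant, but no control or group term. The comparison appears in 8.6 only.

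**The case against.** The strongest reply is that the sentence openly names a historical control. Such controls need not be eligible, recruited or measured here, so zero former controls is not in itself a contradiction. That is right, and the point does not rest on a contradiction. Still, a historical control supports a claim only for the time points it covers, and 8.6 sets no such limit. An analysis plan that is not shown could choose time points and adjustments, but it could not create control values for the 12 months.

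A second reply is grammatical: the phrase could mean both arms of the previous study, which would be a contrast within the parent trial at matching times. That reading is possible. It does not rescue the sentence, because such a contrast says nothing about one-year maintenance. The sentence also sits beside change from baseline over time, in a paragraph about data collected from this study's subjects. It is a further reason to state which arms are meant.

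A third reply concerns weight: no objective, endpoint or specified model uses the old controls. This stands and limits the point.

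A reader might also infer more than the documents support:

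- **That the primary analysis fails because it lacks controls.** The 8.6.1 model does not use the old control arm. Nothing is said here about whether that model is otherwise adequate.
- **That the bias certainly favours FMD.** This depends on the objectives filter, which is in 3.2 but not in the inclusion criteria, and on measuring from the parent baseline.
- **That regression to the mean works against FMD from the new baseline.** T0 is a fresh measurement, so regression due to measurement error would largely have occurred before it. No direction from T0 is shown.
- **That the three-month window in the screening text narrows the timing in step 3.** That window runs to the enrolment period, not to the participant's new baseline, and section 3.2 allows recruitment for up to 3 years.

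**Conclusion.** The point holds. Section 8.6 plans a comparison for which the protocol describes no control data over this study's 12 months, and the parent randomisation does not protect a comparison with earlier control values. Eligible controls: 0; planned control measurements: 0. The final participant value lies 18 to under 24 months after the parent baseline, taking the parent trial's 6 months from section 1.2. The lag of 12 to under 18 months behind the last control value rests on the further assumption of 6 months' follow-up for controls. A tilt towards FMD is claimed only if the 3.2 filter is applied and the parent baseline is used; no size is claimed, and no direction from the new baseline.

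This should be corrected because the sentence bears on what may be concluded. It leaves the objectives, endpoints, stated maximum of 267 and 8.6.1 model untouched.

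**What to change.** In section 8.6, do one of the following:

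- delete the comparison with the previous study's control arm; or
- keep it as a descriptive, non-concurrent external comparison, limited to the time points at which controls were actually measured. State which arms and which baseline it uses, and that it does not support a long-term FMD effect.

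The cost is wording only: no new visits, data or participants, and no change to the planned number. The small downside is that one planned comparison is lost or becomes descriptive only.
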